Although the interventions are not designed to touch on the issue of sexual abusive experiences, there is the possibility that such experiences may be identified during the intervention. In our previous intervention studies, adolescents have not displayed distress over such an experience. However, should it occur we will follow the procedures that the schools would follow if school personnel suspected child abuse. Some schools have a CARE Team that is trained by the Social Welfare and Health Department to identify children who have been sexually or physically abused. If a teacher has reason to suspect that a child has been abused, the teacher informs the CARE Team or the principal. The case is reported to the area social worker. Whether sexual or physical the case would then be reported to the Child Protection Unit at the local police station. The social worker will bring in an appointed medical doctor and rehabilitative services as needed. Some of police stations in the Eastern Cape now have a victim support center (usually used by rape victims), and there are plans for special sections of courts to be set-aside for children's cases. There are also some safe houses in, but nothing like the number needed in light of the prevalence of child abuse and domestic violence.

8. Consent Procedures

A signed parent/guardian consent form is required for adolescents to participate. In addition, participants will sign an adolescent assent form. During recruitment sessions held in the adolescents' school, the Project Director and other project staff will describe the study and invite adolescents to participate. They will then distribute to potential adolescent participants parent/guardian consent forms and cover letters addressed to parent/guardians.

Project staff would return to the school to collect the signed parent/guardian consent forms at a later date before the initial intervention session. Before completing the pre-intervention questionnaire, the participants will be administered the adolescent assent form.

Copies of the parent/guardian consent form and the adolescent assent form are attached.

An additional signed parent/guardian informed consent form and an additional signed adolescent assent form will be required for participation in the long-term follow-up component of the study because this activity was not mentioned in the original consent and assent documents. The project staff will contact the participants, describe the follow-up study and invite adolescents to participate. They will schedule meetings at which the Project Director and the Site Coordinator will meet with participants and their parents/guardians. At these meetings the consent forms and letters will be distributed and read aloud and the follow-up study will be introduced. Where participants attend the meetings without their parents/guardians, they will be given the consent forms and introductory letters to take to their parents or guardians. In cases where the parents cannot read the consent form, the Site Coordinator will read the introductory letter of the study and consent form to them and will obtain their informed consent. The letter will ask the parent/guardian to read and sign the consent form and to give it to the child to return or to return it themselves to the school where the Site Coordinator will meet them on the date indicated in the letter. The Site Coordinator will address any additional questions or concerns on that date.

The consent form will provide sufficient information about the procedures and the risks and benefits of participation to give the parent or guardian a complete understanding and to permit informed consent. The information will be conveyed in a clear, easy to understand manner. A copy of the informed consent document will be given to the parent/guardian. They will also be provided with contact information for Investigators and IRB personnel who can answer questions that may arise in the future.

In addition to parent/guardian informed consent, the adolescents will read and sign an Adolescent Assent Form in order to participate in the long-term follow-up component of the study. Participants will be told that they are volunteering to be in the study and that they can elect not to participate or can withdraw at any time. The participants will read and sign the Assent Form. A copy of the assent document will be given to the participants. They will also be provided with contact information for Investigators and IRB personnel who can answer questions that may arise in the future.

Documentation of informed consent, including signed parent/guardian informed consent forms and adolescent assent forms, will be stored in a locked cabinet to which only authorized personnel have access.

9. Protection of Program Participants

The confidentiality of the information about participants will be maintained. No names or identifying information will be included in research reports. Participants' names will not appear on questionnaires. Participants' names will not appear on the biological specimens. Parents will not be informed of the results of the STD tests. Participants will be given code numbers and

information about them will be organized by code number--not name. The list of code numbers and names will be kept in a locked cabinet accessible only to authorized research staff.

We considered several factors in deciding against notifying parents of the adolescents' STD test results. If the adolescents believed that their parents would be told the results of their tests, the adolescents would be less likely to participate, which could bias the sample through self-selection. Parental notification does not concern protection of research participants, but parental rights. Adolescents who are tested have the opportunity to be treated for a potentially asymptomatic condition, whereas those who do not participate will not have this opportunity. This is a case where participation decreases risk.

10. Potential Benefits

Adolescents may learn about prevention of pregnancy and STDs, including HIV, or other major health risks of South Africans. They will learn ways to protect themselves from these health problems. They may enjoy participating since participants in similar projects have reported enjoying the interventions.

Adolescents will learn whether they have a STD, which may be asymptomatic. In South Africa, STD treatment is based on the presentation of symptoms, not screening. Thus, this study would provide a unique opportunity for the participants to have any asymptomatic STDs identified. STDs can cause pelvic inflammatory disease and infertility and are believed to be a co-factor in HIV transmission. They will receive treatment if they test positive. In addition, adolescents will be referred as appropriate for any mental health problems that become apparent during this research.

There are also benefits that may stem from the proposed research that transcend the individual participants. The participants will contribute to scientific knowledge that could be used to prevent these health problems in South African adolescents. STDs, including HIV, are important health problems affecting the South African community. Unfortunately, efforts to prevent these health problems are constrained by a dearth of hard data on the causes of high-risk behavior.

11. The Risk/Benefit Ratio

The risks of this research are relatively minimal. Considering probability and magnitude, they are not greater than are the risks ordinarily encountered in daily life or during the performance of routine physical and psychological examinations or tests. In contrast, the potential benefits are great. In short, the risks to the individual participants are reasonable in relation to the anticipated benefits to them as individuals and in relation to the importance of the scientific knowledge that will accrue from this research.

The risks of participation in the long-term follow-ups in this research are small relative to the potential benefits. South Africa has more cases of HIV/AIDS than any other country, and the incidence among young people under 20 years of age is extremely high. The risk to the individual participants is reasonable in relation to the anticipated benefits to them as individuals

and in relation to the importance of the scientific knowledge that will accrue from the long-term follow-up component of this research.

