Hypotheses. There are four hypotheses. They include the following:

- To examine whether the students in the HIV/STD intervention schools report less sexual risk behavior than do students in the control schools.
- To examine whether the intervention effects are significantly different among adolescents who vary in pre-intervention sexual experience, age, gender, intimate-partner violence, and sexual abuse history. This information would guide the development of future interventions tailored to subgroups of South African adolescents.
- To examine whether theoretically defined mediators of behavior change (that is, knowledge, behavioral beliefs, normative beliefs, perceived self-efficacy, and intentions) do indeed act as mediators of the intervention's effects on sexual risk behavior.
- To examine whether students in the HIV/STD intervention schools are less likely to test positive for a STD than are students in the control schools.

Statistical Power. Power analysis was performed to determine the sample size needed to detect effects of the interventions on self-reported frequency of unprotected sexual intercourse. We estimated the intracluster correlation coefficient from the pilot data we collected on 6th grade students at 4 schools in Mdantsane. The intracluster correlation for frequency of unprotected sexual intercourse was $\rho = 0.00864$. Assuming $\alpha = .05$, two-tailed, a total of 1,057 6th grade learners from the 18 schools in the trial with an average of 59 students in each school, the estimated power for tests of the effects of interventions on outcomes where the effect size is at least $d = 0.25$ is greater than 99% for attrition rates at the 12 month follow up of 15-20%.

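### The stated power of more than 99% for d = 0.25 does not follow from the protocol's own inputs, which give about 87 to 88%

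*Protocol*

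**What the plan says.** The Statistical Power paragraph in section 1 of the protocol concerns self-reported frequency of unprotected intercourse. It takes an intracluster correlation of 0.00864 from pilot data at four schools. It then sets out its assumptions: "Assuming $\alpha = .05$, two-tailed", and "a total of 1,057 6th grade learners from the 18 schools in the trial with an average of 59 students in each school". For effects of at least d = 0.25 it concludes that power "is greater than 99% for attrition rates at the 12 month follow up of 15-20" percent.

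The total is not in doubt. 18 × 59 = 1,062, which agrees with 1,057 up to rounding of the school average, and sections 1, 3, 4 and 6 all describe 18 schools in the whole trial. Section 1 randomises one school of each matched pair, so there are nine schools per arm. The exception is the caption of Table 1 (the STD power table), which speaks of eighteen matched pairs, that is, 36 schools.

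The paragraph mentions no gain in precision from baseline adjustment, repeated measurements or matching.

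**The concern.** This is the only power statement for the behavioural question, Hypothesis 1. As written, it says that a true effect of 0.25 would be missed less than 1% of the time. A quick bound shows that this cannot be right for a plain two-arm comparison. With 1,057 people split equally, the standard error of a standardised difference is √(4/1,057) = 0.0615, so d = 0.25 lies about 4.06 standard errors from zero. Power above 99% needs about 1.96 + 2.33 = 4.29 standard errors. The figure therefore fails before clustering or attrition is counted. At stake is a true statement of how much protection against a missed effect the design offers.

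**Working it through.** **Inputs, all from the Statistical Power paragraph:** N = 1,057 in total; 18 schools; ρ = 0.00864; two-sided α = 0.05; d = 0.25; attrition 15% and 20%. Equal allocation follows from the matched-pair randomisation in section 1.

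**Formulas.** Retained N = 1,057 × (1 − attrition). Mean school size m = N/18. Design effect DE = 1 + (m − 1)ρ. Effective N = N/DE. SE(d) = √(4/effective N). Power = Φ(d/SE − 1.96).

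**Attempt to reproduce the stated figure:**

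| | 15% attrition | 20% attrition |
|---|---|---|
| Retained N | 898 | 846 |
| m | 49.9 | 47.0 |
| DE | 1.423 | 1.397 |
| Effective N | 632 | 605 |
| SE(d) | 0.0796 | 0.0813 |
| d/SE | 3.14 | 3.08 |
| Power | 0.881 | 0.868 |

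More than 99% is not reproduced.

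**Variants that keep 1,057 learners:**

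| Variant | 15% attrition | 20% attrition |
|---|---|---|
| One-sided test | 0.933 | 0.924 |
| Clustering ignored (ρ = 0) | 0.963 | 0.953 |
| ρ with a misplaced decimal (0.000864) | 0.956 | 0.946 |
| Same 1,057 learners in 36 schools | 0.927 | 0.914 |

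Without attrition, power is 0.913 with the stated ρ and 0.982 with ρ = 0. The last is the ceiling for an unadjusted comparison at one time point.

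**Effect at which 99% is reached.** d = (1.96 + 2.33) × SE(d). This gives 4.29 × 0.0796 = 0.34 at 15% attrition and 4.29 × 0.0813 = 0.35 at 20%.

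**Doubling the trial.** With 36 schools and 2 × 1,057 = 2,114 learners, m and DE are unchanged and the effective N doubles to 1,263 and 1,210. Then d/SE is 4.44 and 4.35, and power is 0.993 and 0.992, which agrees with the stated figure. Doubling only the learners (1,057 per arm, still 18 schools) gives 0.973 and 0.969, which does not.

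**Small-sample reference.** The calculation above uses the normal distribution. With 18 clusters a t reference at school level is more cautious. With 16 degrees of freedom (18 schools less two arms), power is 0.838 and 0.823. With 8 (nine matched pairs less one), it is 0.785 and 0.768.

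**The case against.** The strongest reply is that the protocol does not print its formula, and that Hypothesis 1 is to be analysed by GEE over several waves. A repeated-measures calculation might therefore lie behind the figure. Suppose three follow-ups are averaged and the whole variance, school component included, shrinks by (1 + 2r)/3. A within-person correlation of r = 0.2 then gives 99.6% and 99.4% (15% and 20% attrition), and r = 0.3 gives 99.0% and 98.8%. Baseline adjustment reaches 99% if the baseline-outcome correlation is about 0.68 to 0.70.

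Part of this stands. It shows that doubling the trial is not the only route to about 99%. It does not rescue the sentence, because the paragraph states none of these assumptions and ties its figure to attrition at the single 12-month visit. If averaging reduces only the within-school variance, power stays at about 96 to 98% for the same correlations. A baseline correlation near 0.7 is also hard to expect when the protocol reports that only 3.3% were sexually experienced at baseline.

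A reader might infer that the figure was certainly obtained by treating 1,057 learners and 18 schools as the size of each arm. The match at 99.2 to 99.3% and the Table 1 caption make this plausible. Table 1 adds some support: for 0.154 against 0.09, N = 809 and 20% attrition it prints 0.88, where 809 in 18 schools gives 0.59 and 809 per arm in 36 schools gives 0.87. But without the formula this remains an inference, and the error does not depend on it.

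It is also fair to say that the number enrolled is already settled and that a null result will be read mainly from its confidence interval. That limits the consequence; it does not make the printed figure right.

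**Conclusion.** The stated power is wrong for the stated inputs. The standard calculation gives about 88% at 15% attrition and 87% at 20%, so the chance of missing d = 0.25 is about 12 to 13%, not under 1%. This rests on equal allocation, equal school sizes, the pilot ρ of 0.00864, and an unadjusted comparison at one time point with a normal reference. The normal reference is the favourable choice. The conclusion that the figure is overstated does not depend on ρ, because the ceiling with ρ = 0 and no attrition is 98.2%.

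A reader might go further and conclude that the behavioural comparison is underpowered. The documents do not support that: 87 to 88% is adequate, and 82 to 84% with 16 degrees of freedom still exceeds the usual 80%. Only the 8-degree-of-freedom reading falls slightly below 80%, and the protocol plans GEE without naming any t reference, so neither reading can be called the trial's power.

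**What to change.** Restate the sentence so that power for d = 0.25 is about 87 to 88% at 15 to 20% attrition, and add that 99% is reached only at d of about 0.34 to 0.35. Note that the figure uses a normal reference and falls with a small-sample school-level one: about 82 to 84% with 16 degrees of freedom, and about 77 to 79% with 8 if the matched pairs are analysed as pairs. Alternatively, if more than 99% came from a calculation with repeated measures or baseline adjustment, state that method and the correlations assumed. Whichever is chosen, make clear whether 1,057 and 18 are totals or per-arm numbers, and reconcile the Table 1 caption with the 18 schools given elsewhere.

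The cost is one or two sentences of protocol text and a less favourable figure. The sample size, the design and the conduct of the trial need not change.

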University of Pennsylvania
Institutional Review Board (IRB) Application
Protocol Summary Outline

Date: May 4, 2009

Principal Investigator: [name]

Responsible Organization: Annenberg School for Communication

Protocol Title: South African Adolescent Health Promotion Project

Protocol #: 705388

1. Purpose

South African adolescents are at high risk for HIV infection because of unprotected sexual intercourse. What is needed is research to develop, implement, and test interventions to reduce South African adolescents' behaviors associated with this risk. Results of controlled studies in the US indicate that behavioral interventions, including the Be Proud! Be Responsible! curriculum, have reduced HIV sexual risk behavior among adolescents. Unfortunately, the available research literature contains few randomized controlled trials testing such interventions in sub-Saharan Africa and only one in South Africa.

The broad objective of the proposed research is to identify effective, sustainable interventions to dissuade South African adolescents from engaging in behaviors that increase their risk for sexually transmitted diseases (STDs), including HIV.

The participants will be 1,057 6th grade Xhosa speaking South African adolescents at 18 senior primary schools in Mdantsane and Berlin, Eastern Cape Province, South Africa. Matched pairs of schools will be randomly selected from among the senior primary schools that agree to participate in the study. The schools will be paired based on their similarity of the following factors: estimated number of 6th grade learners, number of classrooms with electrical outlets (a proxy for socioeconomic status), and the number of classrooms at each school. Additionally, rural and urban schools will be paired separately based on these criteria. One school in each pair selected will be randomly assigned to receive one of two interventions: (a) an HIV/STD risk-reduction intervention; or (b) a general health promotion intervention concerning health issues unrelated to sexual behavior, which will serve as the control condition.

The HIV/STD risk reduction intervention will be adapted from the Be Proud! Be Responsible! curricula found to be effective with African American adolescents in the U.S. This approach will draw on social cognitive theory, the theory of reasoned action/theory of planned behavior, and our previous risk-reduction research with inner-city African American adolescents.

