We also estimated statistical power for STD incidence specifically. Some of the participants will be sexually experienced at the time of the follow-ups and therefore at risk of STD, but others will not be sexually experienced and therefore not at risk for STD. The power analysis for STD incidence must take into account the size of sample that is at risk. The median age of first sexual intercourse in South Africa is about 16 (MacPhail et al., 2002; Manzini, 2001; Richter et al., 2005; Simbayi et al., 2004). At baseline 76.54% of the adolescents in our study were 12 years or older and therefore will be 16 years or older at the 54-month follow-up. We considered three different rates of sexual experience and risk for STD at the 54-month follow-up: 76.5% (N=809), 51.3% (N=542), and 38.3% (N=405) of the original 1,057 participants.

Based on previous studies (Auvert et al., 2001; Johnson et al., 2005), we estimated that about 15.4% of the sexually experienced participants in the absence of a HIV/STD risk-reduction intervention would test positive for CT, GC, or TV at either the 42-month or the 54-month follow-up. We estimated power for detecting significant differences in STD incidence over the follow-up period for attrition rates of 15% and 20% at the 54-month follow-up, $\rho = 0.009$, and STD incidence in the health-promotion control group = 0.154. At baseline, only 3.3% of participants were sexually experienced; hence, for the other 96% of participants, any STDs we detect will have been contracted during the follow-up period. The study is well powered to detect incidence differences in the range of at least 6.4% to 8.4%, depending on the true proportion of sexually experienced adolescents in the sample at the 54-month follow-up. Table 1 presents a range of estimates based on 38.3% to 76.5% of the baseline sample contributing to the STI incidence endpoint at the 54-month follow-up.

Table 1. Estimated power to detect a decrease in STD incidence assuming a cluster randomized controlled trial with a total of N=809, N=542, and N=405 sexually experienced participants enrolled from 18 matched pairs of schools (alpha = 0.05, two-tailed, rho = 0.009).

STD incidence			Attrition rate (54 months)					
			20%			15%		
Control	Intervention	Difference	N=809	N=542	N=405	N=809	N=542	N=405
0.154	0.10	0.054	0.76	0.58	0.47	0.78	0.61	0.49
0.154	0.09	0.064	0.88	0.73	0.60	0.90	0.75	0.63
0.154	0.08	0.074	0.95	0.84	0.72	0.96	0.86	0.74
0.154	0.07	0.084	0.98	0.91	0.81	0.99	0.93	0.84

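### STD power rests on one unsourced intracluster correlation (0.009) that Table 1 never varies; recompute the table on 18 schools and total N over an ICC range

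*Protocol*

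**What the plan says.** All of this is in the Protocol, Section 1, under Statistical Power.

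- **Self-report calculation.** The only ICC with a stated origin is 0.00864, for frequency of unprotected intercourse. Its origin: "We estimated the intracluster correlation coefficient from the pilot data we collected on 6th grade students at 4 schools in Mdantsane".
- **STD calculation.** Power is given "for attrition rates of 15% and 20% at the 54-month follow-up, $\rho = 0.009$, and STD incidence in the health-promotion control group = 0.154". The text does not say where 0.009 comes from. The control rate is the share of sexually experienced participants who "would test positive for CT, GC, or TV at either the 42-month or the 54-month follow-up".
- **Table 1.** The caption describes a "total of N=809, N=542, and N=405 sexually experienced participants enrolled from 18 matched pairs of schools (alpha = 0.05, two-tailed, rho = 0.009"). The table varies the at-risk N, the attrition and the intervention rate, but not rho.
- **Conclusion drawn.** The study is called well powered for differences of 6.4 to 8.4 percentage points, depending on how many participants are sexually experienced by 54 months.
- **Size of the trial.** Section 1 enrols "6th grade Xhosa speaking South African adolescents at 18 senior primary schools in Mdantsane and Berlin", paired, so 9 pairs.

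**The concern.** The protocol treats STD as needing its own power calculation and redoes the at-risk sample for it, but gives no separate reasoning for the clustering parameter. That 0.009 is the rounded pilot value is an inference; the protocol does not say so. If it is, the value was carried over from a different measure (self-reported frequency, not a laboratory-confirmed binary result), a younger group (6th graders, not sexually experienced adolescents at 42 to 54 months) and 4 schools in Mdantsane only. If it is not, the value has no stated basis.

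Either way, one unverified number stands behind every cell of Table 1 and behind the claim of good power. If that claim is taken at face value, a non-significant result on Hypothesis 4 could be given more weight as evidence of no effect than the design can carry.

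**Working it through.** **Inputs.** From the protocol: two-sided alpha 0.05; control rate p1 = 0.154; intervention rates p2 = 0.09, 0.08, 0.07; at-risk N = 809, 542, 405; attrition 20%; rho = 0.009; 18 schools. N is a total: 0.765 × 1,057 = 809. Assumed: rho values other than 0.009, and pilot size.

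**Formulas.** Analysable n = 0.8N; average cluster size m = n/18; design effect DE = 1 + (m − 1)rho; effective number per arm n₁ = (n/2)/DE; SE = √{[p1(1 − p1) + p2(1 − p2)]/n₁}; power = Φ[(p1 − p2)/SE − 1.96].

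**Step 1: the plan's own figure.** For N=809 and 0.154 versus 0.09: n = 647.2, m = 35.96, DE = 1 + 34.96 × 0.009 = 1.315, n₁ = 323.6/1.315 = 246.2, SE = √(0.2122/246.2) = 0.0294. Then 0.064/0.0294 = 2.18 and power = Φ(0.22) = 0.59. Table 1 prints 0.88. At rho = 0, n₁ = 323.6, SE = 0.0256 and power is only 0.71. The printed table therefore does not follow from its stated totals at any non-negative rho.

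**Step 2: sensitivity to rho.** The first three rows are the cells behind the 6.4 to 8.4 point claim (N as total, 18 schools, 20% attrition).

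| N | p2 | Printed | rho 0 | 0.009 | 0.02 | 0.03 |
|---|---|---|---|---|---|---|
| 809 | 0.09 | 0.88 | 0.71 | 0.59 | 0.48 | 0.42 |
| 542 | 0.08 | 0.84 | 0.67 | 0.59 | 0.51 | 0.46 |
| 405 | 0.07 | 0.81 | 0.68 | 0.62 | 0.55 | 0.50 |
| 809 | 0.07 | 0.98 | 0.93 | 0.85 | 0.75 | 0.67 |

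A pooled-variance version of the test changes these by at most 0.01.

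**Step 3: the basis that comes closest to the printed table.** Reading N as per arm, with 36 schools, gives 0.87 at rho 0.009 for N=809 and 0.154 versus 0.09 (printed 0.88). It does not match every cell: N=405 with 0.07 gives 0.89 (printed 0.81). On this basis the first cell falls to 0.77 at rho 0.02 and 0.70 at 0.03; the second falls to 0.84 and 0.80.

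**Step 4: precision of the pilot value.** For k = 4 schools of m pupils, F = 1 + m × 0.00864/(1 − 0.00864), with 3 and 4(m − 1) degrees of freedom. Dividing F by its 97.5% and 2.5% points gives limits F*, and each converts to an ICC by (F* − 1)/(F* + m − 1).

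- m = 30: F = 1.26, interval −0.02 to 0.36.
- m = 60: F = 1.52, interval −0.01 to 0.25.

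The interval assumes roughly normal data, so it is only a guide for a skewed frequency measure.

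**The case against.** A reader might infer more: that 0.009 understates clustering of STD, and that this is why Table 1 overstates power. The documents support neither step.

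**Direction.** The argument for a higher ICC is that a binary outcome's ICC shrinks when the outcome is rare, and "At baseline, only 3.3% of participants were sexually experienced". Holding between-school variation constant on the probit scale, 0.00864 at a rate of 3.3% becomes 0.022 at 15.4%. But the pilot measure was a frequency, not a binary outcome. The 3.3% is sexual experience in the trial sample, not unprotected intercourse in the pilot, and it is a share of all pupils, while 15.4% is a share of the sexually experienced. The pilot rate is not given: at 2%, 5% and 10% the same formula returns 0.031, 0.017 and 0.011. There are also reasons for a lower ICC. Participants may be at high schools by then (Section 3, long-term follow-up), which could dilute clustering by primary school, and restricting to the sexually experienced removes school differences in sexual debut. The interval in Step 4 shows imprecision, not downward bias.

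**Cause.** Step 1 settles this: the printed powers are out of reach even with no clustering. The likelier source is the sample basis. A total N seems to have been used as roughly a per-arm number, and the caption's 18 pairs would mean 36 schools where the trial has 18.

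**Weight.** STD is a secondary outcome (Section 6) and the cohort is fixed. On the per-arm basis the 8.4 point claim at N=405 still has power 0.84 at rho 0.02. The at-risk N also matters more than rho in places: at rho 0.009 and p2 = 0.07, going from N=809 to N=405 takes power from 0.85 to 0.62.

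All of this stands. What it leaves untouched is that rho is unsourced for STD, was never varied, and moves the stated power materially.

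**Conclusion.** The point holds as a gap in the stated power: one unsourced ICC, probably taken from a 4-school pilot on another outcome, is treated as known. On total N and 18 schools, moving rho from 0.009 to 0.02 or 0.03 takes 0.154 versus 0.09 at N=809 from 0.59 to 0.48 or 0.42, and 0.154 versus 0.07 from 0.85 to 0.75 or 0.67. At rho 0.02 even the 8.4 point difference at the largest N falls short of 80%.

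It does not hold as a claim that the true STD ICC exceeds 0.009, or that rho explains the size of the printed powers. Correcting rho alone would leave the larger error in the sample basis; correcting the sample basis alone would leave rho untested.

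The figures assume equal cluster sizes, a normal reference and no gain from matching. The values 0.02 and 0.03 are assumptions, since the protocol gives no STD ICC.

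**What to change.** 1. Recompute Table 1 with N as the total and 18 schools (9 pairs), and correct the caption to match.
2. State where 0.009 comes from, and show the table over a range of ICCs, for example 0.01, 0.02 and 0.03, labelled as assumptions. By the formulas above, at 20% attrition, the three cells behind the present claim become 0.58 / 0.48 / 0.42 (N=809, 6.4 points), 0.59 / 0.51 / 0.46 (N=542, 7.4 points) and 0.61 / 0.55 / 0.50 (N=405, 8.4 points).
3. Restate the detectable difference and replace the sentence on good power with one that the recomputed table supports.
4. Where the trial's own follow-up data from the 18 schools are available, estimate the ICC within arm from binary sexual-behavior outcomes to choose the central value. This gives 16 between-school degrees of freedom instead of 3. Say plainly that it is still a self-reported proxy, measured before the STD endpoint.

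The cost is a recalculated table and a revised paragraph, with no new data and no one extra enrolled. The downside is a less favourable stated power.

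### Table 1 overstates STD power in all 24 cells: its caption has 18 pairs of schools where the trial has 9, and its powers fit a trial about twice this size

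*Protocol*

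**What the plan says.** Protocol section 1 (Purpose) sets the size of the trial: "1,057 6th grade Xhosa speaking South African adolescents at 18 senior primary schools in Mdantsane and Berlin". Schools are matched in pairs, and "One school in each pair selected will be randomly assigned to receive one of two interventions". Eighteen schools make 9 pairs, with 9 schools in each arm. Section 3 repeats the 18 schools, with about 59 participants in each.

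The STD power calculation, under Statistical Power in section 1, takes three possible numbers of sexually experienced participants at 54 months: "76.5% (N=809), 51.3% (N=542), and 38.3% (N=405) of the original 1,057 participants". Its other inputs are "alpha = 0.05, two-tailed, rho = 0.009", attrition of 15% or 20%, and "STD incidence in the health-promotion control group = 0.154".

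The caption of Table 1 then describes "a total of N=809, N=542, and N=405 sexually experienced participants enrolled from 18 matched pairs of schools". The text concludes: "The study is well powered to detect incidence differences in the range of at least 6.4% to 8.4" per cent, depending on the share who are sexually experienced. In the table, 6.4, 7.4 and 8.4 points are the first rows at which the columns for N=809, N=542 and N=405 respectively pass 0.80. The claim therefore pairs the smallest difference with the largest N and the largest difference with the smallest N.

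**The concern.** Eighteen matched pairs would be 36 schools, twice the number in the trial. If this were only a slip in the caption, the powers would still come out with 9 schools per arm and N split over two arms. They do not, so the error is in the numbers as well as the wording.

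The table is the only quantitative support for Hypothesis 4, which concerns the trial's one biologically measured endpoint. A reader who trusts it could take a non-significant result as evidence against a 6.4 to 8.4 point reduction, when the trial would miss such a reduction about four times in ten at the protocol's own pairings.

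**Working it through.** **Inputs (all from protocol section 1).** Control incidence p1 = 0.154; intervention incidence p2 = 0.10, 0.09, 0.08 or 0.07; intracluster correlation 0.009; two-sided alpha 0.05; attrition a = 20% or 15%; N = 809, 542 or 405 over both arms; 9 schools per arm.

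**Formulas.**
- Analysed per arm: n = N(1 − a)/2
- Mean per school: m = n/9
- Design effect: DE = 1 + (m − 1) × 0.009
- SE = √{[p1(1 − p1) + p2(1 − p2)] × DE/n}
- Power = Φ[(p1 − p2)/SE − 1.96]

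**Worked cell: N=809, 20% attrition, 0.154 v 0.09.** n = 809 × 0.80/2 = 323.6; m = 35.96; DE = 1.315; SE = 0.0294; 0.064/0.0294 = 2.18; power = Φ(0.22) = 0.59. The table prints 0.88.

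**The protocol's three pairings, at 20%/15% attrition.**

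| Difference | N | Printed | Recomputed, 9 schools per arm | No clustering |
|---|---|---|---|---|
| 6.4 points | 809 | 0.88/0.90 | 0.59/0.61 | 0.71/0.73 |
| 7.4 points | 542 | 0.84/0.86 | 0.59/0.61 | 0.68/0.70 |
| 8.4 points | 405 | 0.81/0.84 | 0.62/0.64 | 0.68/0.70 |

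**All 24 cells.** Every printed value is too high, by 0.13 to 0.33 (mean 0.23). Twelve printed cells reach 0.80; two recomputed cells do, both for 8.4 points with N=809 (0.85/0.86). A t reference with 16 degrees of freedom lowers power at the three pairings by about 0.05.

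**Can the printed table be obtained with N as a total?**
- With clustering removed, every printed cell is still 0.05 to 0.22 too high.
- With clustering and attrition both removed, the three pairings give 0.80, 0.77 and 0.77, still below the printed 20%-attrition values of 0.88, 0.84 and 0.81.
- With the school count doubled to 18 per arm and N kept as a total, every cell still falls short, by up to 0.27.
- Pooled, unpooled and arcsine variances agree closely, so the choice of formula does not explain the gap.

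**What does come close?** Taking N per arm with 18 schools per arm, the worked cell has n = 647.2, m = 35.96, DE = 1.315 and power 0.87, against 0.88 printed. Over all cells this calculation averages 0.02 above the table, with a largest gap of 0.08. N per arm with a t reference on 34 degrees of freedom (18 schools per arm), the control variance in both arms and no design effect matches all 24 cells within 0.016.

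**Detectable differences at 80% power** (normal reference, 9 schools per arm, 20%/15% attrition): 8.0/7.8 points for N=809, 9.1/8.9 for N=542 and 10.1/9.9 for N=405. With the t reference on 16 degrees of freedom they are 8.4/8.2, 9.6/9.4 and 10.6/10.4.

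**The case against.** The strongest reply is that the cause is not proven. The protocol nowhere says that N is per arm, and the software is not named. The standard design-effect formula with doubled inputs misses some cells by 0.08, and the variant that fits every cell drops the design effect, which would be a different error. A one-sided calculation with total N, no clustering and no attrition also comes near the table (largest gap 0.045). That is right as far as it goes: the doubling is the best-supported explanation, not a documented fact. The one-sided route, however, contradicts the stated two-tailed test and cannot produce different values at 15% and 20% attrition. In any case the finding does not depend on the cause, because the caption contradicts the design and no cell is attainable from the stated inputs.

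Secondly, power of about 0.60 describes three pairings. It is 0.85/0.86 for 8.4 points with N=809 and 0.38/0.39 for 6.4 points with N=405. This is true, but the three pairings are the ones the protocol's sentence rests on.

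Thirdly, matching might recover some precision. It can at most remove the between-school variance, and the no-clustering figures already set that to zero.

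Finally, section 6 calls STD incidence a secondary outcome, the main sample-size calculation was for unprotected intercourse, and the correction alters neither enrolment nor analysis. That limits the consequence but does not make the table right. Section 6 also adds HSV-2 to the endpoint, while 0.154 covers only chlamydia, gonorrhoea and trichomonas. Any restated figure is therefore conditional on 0.154.

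**Conclusion.** The concern holds. The caption's 18 pairs contradict the trial's 18 schools, and all 24 powers are too high for a trial of this size, by 0.13 to 0.33. At the pairings behind the protocol's claim, power is about 0.59 to 0.64, not 0.81 to 0.90, and 80% power needs differences of about 8 to 10 points.

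These figures assume the protocol's control incidence of 0.154 and correlation of 0.009, equal numbers per arm and per school, a normal reference (a t reference is less favourable), and no credit for matching. That the table was computed with N and 18 schools per arm is an inference from the fit.

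**What to change.** - Correct the Table 1 caption to 18 schools in 9 matched pairs.
- Recompute all cells with N as the total over both arms and 9 schools per arm, and state the method and reference distribution used.
- Replace the sentence on being well powered. Suggested wording: at a control incidence of 0.154 and 20% attrition, the trial has 80% power for a difference of about 8 points if 76.5% of participants are sexually experienced, about 9 points if 51.3% are, and about 10 points if 38.3% are; a non-significant result does not rule out smaller effects.
- Recheck the figure of more than 99% for d = 0.25 in the same section. With 1,057 in total, 9 schools per arm and correlation 0.00864, power is about 0.88 at 15% and 0.87 at 20% attrition; it reaches 0.99 only if 1,057 participants and 18 schools are counted per arm.

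The cost is a corrected table and a reworded sentence, with a less favourable stated power. Participants, allocation, endpoint and analysis are unchanged.
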